### **I. Abstract**

Postoperative ileus and opioid induced constipation are well-known post-operative complications. Previously, research has shown that using peripherally acting opioid antagonists can help alleviate the condition. There has not been a prospective study to investigate whether use of peripherally acting opioid antagonists are effective in preventing post-operative ileus in patients having spinal fusion surgeries.

### **II. Background and Significance/Preliminary Studies**

Post-operative ileus is a well-recognized entity and can significantly prolong a patients' length of stay in the hospital. Anterior surgical approaches and duration of surgery for spinal fusion have been shown to increase the incidence of post-operative ileus with no successful intervention identified that reduces the incidence of ileus.

Naloxone is an opioid antagonist which is FDA approved as an intravenous agent for the reversal of adverse effects associated with synthetic and naturally occurring opioid agonists. Enteral administration of naloxone has been investigated for the reversal of opioid induced constipation. Naloxone administered via the enteral route has been shown to antagonize the effect of opioid medications peripherally without affecting pain control. There was a significant increase in bowel movements and reduction in laxative use without a significant impact on pain control.

### **I. Study Aims**

The current study will assess the safety and efficacy of an enteral formulation of the opioid antagonist naloxone in prevention of post-operative ileus and opioid induced constipation.

### **I. Administrative Organization**

This is a single center study to be completed at Loyola University Medical Center. Participants may be located on a number of different in-patient units including Neurosciences Intensive Care Unit (2W), Surgical Intensive Care Unit (4N/S/WICU), Cardiac Care Unit (3HTU), Progressive Care unit (2N/PCU), and medical-surgical wards (2E or 4T).

### **I. Study Design**

This is a prospective, historically controlled observational trial of enteral naloxone use in patients admitted for spinal fusion surgery and receiving opioids for pain management.

Primary outcome: Time to first bowel movement (hours)

Secondary outcomes:

- Hospital length of stay
- Incidence of post-operative ileus. Post-operative ileus will be diagnosed through a combination of clinical exam and radiographic (X-ray) findings
- incidence of post-operative constipation (defined as 3 days without a bowel movement)
- average numerical pain scale (Adult Nonverbal Pain scale or Visual Analog Scale) on post-operative days 0, 1, 2, and 3
- average daily opioid requirement on post-operative days 0, 1, 2 and 3 (morphine equivalents)
- number of naloxone doses administered
- average number of daily bowel movements,
- number of medication escalations required (defined as use of an as needed laxative medication or addition of a new order for a laxative medication)
- Incidence of adverse effects
- Incidence of study drug discontinuation

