### Screening procedures

Patients will be screened at the pre-operative clinic visit based on the inclusion and exclusion criteria.

Historical controls will be identified by a report of patients undergoing spinal fusion procedures

identified via ICD9 codes in the previous 3 years. ICD-9 codes include a short fusion surgery (81.06, 81.62) with 3 or fewer vertebral body segments, long fusion surgery (81.63, 81.64), more than 4 vertebral segments, anterior approaches (81.06) and posterior approaches (81.07) in the thoracic and lumbar spine. The historical controls will be matched to active participants based on age, gender, Charleston co-morbidity index, complexity of surgery, and duration of surgery.

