### Study Intervention

Active study agents: Naloxone

Blinding/labeling/preparation of agents: No blinding is required in this study. The study drug will be prepared, unit dose labelled, and patient labelled according to institutional protocols.

Storage: Secured at room temperature in the central pharmacy then dispensed as a patient specific supply and stored at room temperature the automated dispensing cabinet. No more than a 24 hour supply will be dispensed at any given time.

Administration: 4 mg of a 1 mg/ml oral solution administered enterally (oral, nasogastric, orogastric, gastrostomy, or jejunostomy) every 8 hours for 48 hours

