### Study Assessments and Activities

All patients will undergo the scheduled operation per routine. Post operatively, all usual medications for pain control and bowel movements will be ordered according to institutionally approved and reviewed post-operative order sets. All home medications will also be reconciled and restarted as deemed clinically appropriate by the interdisciplinary care team. Oral naloxone 4 mg enterally every 8 hours will be initiated on post-operative day 1 at 0900. Study drug will be discontinued as described in the study protocol, after 48 hours, or upon discharge whichever is sooner.

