#### Analysis Plan

Two different approaches will be used for the primary aim. First, a paired *t*-test will be used to estimate the mean difference in hours to first feces between the active cohort and historical control cohort. For this analysis, the origin of time for both groups is start of surgery. If necessary, a Wilcoxon signed ranks test will be used to compare the two distributions.

A second approach will compare the instantaneous rates of bowel movements between the active and control cohorts using a Frailty survival model that allows for clustering of patients within their matched strata. In this analysis, control patients who required treatment for ileus will be censored at the time of such treatment, and active patients who require an additional treatment beyond receipt of naloxone will be censored at the time of such treatment. All patients who do not achieve BM by 120 hours will also be censored. Hours to first feces for both groups will be start of surgery. While we assume there is no immortal time bias between start of surgery and receipt of naloxone for the active cohort, a conditional landmark method may be used to account for the amount of hours between surgery and receipt of naloxone. The proportional hazards assumption for all predictors will be tested using Martingale residuals as described by Lin, Wei, and Ying.

Regarding the secondary aims, a linear mixed effects model will be used to compare LOS between the two groups. A generalized linear mixed effects model will be used to compare the two groups on all other secondary outcomes. In these models, random intercepts will be allowed for each case-control matched strata in order to account for the correlation between cases and controls based on age, gender, Charleston co-morbidity index, and operation time under anesthesia.

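### Constipation is analysed as yes/no over 3 days, but patients discharged without a bowel movement before 72 hours have no observed outcome and no scoring rule

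*Combined protocol and SAP*

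**What the plan says.** I. Study Design names among the secondary outcomes the "incidence of post-operative constipation (defined as 3 days without a bowel movement"). It does not say when the three days start or what happens if observation ends before they are over. The Analysis Plan models length of stay separately and then states: "A generalized linear mixed effects model will be used to compare the two groups on all other secondary outcomes". Random intercepts for the matched strata are specified. A rule for incomplete observation of this outcome is not.

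Study Assessments and Activities starts the study drug at 0900 on post-operative day 1 and ends it as follows: "Study drug will be discontinued as described in the study protocol, after 48 hours, or upon discharge whichever is sooner". No section describes recording BMs after discharge.

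Three further statements bear on comparability. Controls are historical, "identified via ICD9 codes in the previous 3 years" (Screening procedures). On blinding, Study Intervention says "No blinding is required in this study". Bowel medication follows routine care: "all usual medications for pain control and bowel movements will be ordered according to institutionally approved and reviewed post-operative order sets". Laxative use is a separate secondary outcome, the "number of medication escalations required (defined as use of an as needed laxative medication or addition of a new order for a laxative medication"), and is not part of the constipation definition.

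**The concern.** Only some patients can become unscorable. One who has a BM and then goes home on day 2 is already known not to be constipated. One who goes home on day 2 without a BM could still turn out either way. The missing outcomes therefore fall entirely on patients who were BM-free when last seen, so dropping them is not neutral, and calling them all no or all yes is wrong for part of them.

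If both cohorts left hospital on the same schedule, the errors would largely cancel in the comparison, although the reported incidences would still be off. Equal schedules cannot be assumed. Length of stay is itself an outcome that naloxone might shorten, and the controls come from earlier years. Prevention of opioid-induced constipation is a stated study aim, and this is the only outcome defined as constipation. Without a rule, the choice of coding would be made after the data are seen.

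**Working it through.** **Inputs from the Power Analysis:** BM rates of 0.160 per day (control) and 0.241 per day (naloxone); hazard ratio 1.508; 150 patients per cohort; two-sided alpha 0.05; stated power 80.1%.

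**Assumptions, not in the documents:** exponential times to first BM; the three days read as the first 72 hours; a fraction *d* of a cohort discharged at day 2, independently of bowel function.

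**1. The plan's own figure.** Expected events = 150 × (1 − e^(−0.80)) + 150 × (1 − e^(−1.205)) = 82.6 + 105.0 = 187.6. Schoenfeld power = Φ(½ × √187.6 × ln 1.508 − 1.96) = Φ(0.85) = 80.3%, against 80.1% stated. The rates are being read as the plan intends.

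**2. What they imply at 3 days.** BM-free: e^(−0.48) = 61.9% for control and e^(−0.723) = 48.5% for naloxone, a planned difference of 13.3 points.

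**3. The window.** Day 1 at 0900 plus 48 hours is day 3 at 0900, roughly 72 hours after a morning operation. A clause that ends dosing at discharge if that is sooner therefore foresees discharge before the three days are complete.

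**4. Effect of each coding, no drug effect, 0.160 per day in both cohorts.** BM-free at day 2 is e^(−0.32) = 72.6%.
- Unscorable share: u = d × 0.726
- Scored as no: (1 − d) × 0.619
- Scored as yes: (1 − d) × 0.619 + u
- Excluded: (1 − d) × 0.619 / (1 − u)

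| Discharged at day 2 | Unscorable | Scored as no | Excluded | Scored as yes |
|---|---|---|---|---|
| 10% | 7.3% | 55.7% | 60.1% | 63.0% |
| 20% | 14.5% | 49.5% | 57.9% | 64.0% |
| 30% | 21.8% | 43.3% | 55.4% | 65.1% |

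The truth is 61.9% in every row. With 10% in one cohort and 30% in the other, the false difference is 12.4 points (no), 4.7 points (excluded) or 2.1 points in the opposite direction (yes).

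For the first, SE = √[(0.557 × 0.443 + 0.433 × 0.567)/150] = 0.057, so 12.4 points is about 2.2 SE. An unmatched two-proportion test, with pooled SE √(2 × 0.495 × 0.505/150) = 0.0577, would reject with probability Φ((0.124 − 1.96 × 0.0577)/0.0573), about 57%.

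**5. The reverse case.** With the plan's effect present, 30% of controls and 10% of naloxone patients leaving at day 2, and those BM-free scored as no: 0.7 × 0.619 = 43.3% versus 0.9 × 0.485 = 43.7%. The planned 13.3 points disappear.

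**6. Censoring at discharge.** Kaplan-Meier at 72 hours estimates e^(−0.32) × e^(−0.16) = 0.726 × 0.852 = 61.9% for any *d*, so the false difference is zero if discharge is independent of BM.

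**7. Side check on rescue laxatives.** No drug effect; an assumed 20% versus 40% of BM-free patients rescued; rescue multiplies the BM hazard by *k*. The composite is no BM by 72 hours or a laxative escalation before the first BM.
- Rescue at 48 hours, current definition: 0.726 × 0.2 × (0.852 − e^(−0.16k)) = 1.0, 1.8 and 3.4 points for k = 1.5, 2 and 3.
- Rescue at 48 hours, composite: 0.726 × 0.2 × (1 − 0.852) = 2.1 points.
- Rescue at 24 hours, current definition: 0.852 × 0.2 × (0.726 − e^(−0.32k)) = 1.8 and 3.4 points for k = 1.5 and 2.
- Rescue at 24 hours, composite: 0.852 × 0.2 × (1 − 0.726) = 4.7 points.

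The two definitions err in opposite directions: the current one favours the cohort rescued more, and the composite penalises it.

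**The case against.** The strongest objection is that the discharge clause is only a drug-stopping rule. It gives no rate, and if few patients leave BM-free before 72 hours, or equally many in each cohort, the comparison is hardly affected. That stands: the size is illustrative, and this is one of ten secondary outcomes. It does not remove the gap, because the plan neither describes later follow-up nor says how such patients are scored.

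A reader might infer that these patients default to not constipated. The plan does not say so; that coding is only the one with the largest error here.

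A reader might also infer that the endpoint is biased by rescue: a patient given a laxative on day 2 who then passes stool counts as a success, so the cohort rescued earlier looks better. The documents do not support that as a finding. They do not show that rescue practice differed or in which direction, and care follows institutional order sets at a single centre. False differences of 5 to 8 points at 20% versus 40% rescue at 48 hours need a BM within 24 hours in 50% to 70% of those rescued, against a natural 15%. That is a hazard multiplier of −ln(0.5)/0.16 = 4.3 to −ln(0.3)/0.16 = 7.5. At multipliers of 1.5 to 3 the bias is 1.0 to 3.4 points.

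Nor is there a clean contradiction with the primary analysis. The frailty model censors active patients at any additional treatment but controls only at treatment for ileus, and no rescue censoring is stated for the paired *t*-test. Counting any BM, however achieved, is a legitimate treatment-policy outcome, and the separate escalation count would make an imbalance visible.

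**Conclusion.** The point holds for discharge. The plan treats constipation as fully observed for three days when its own dosing rule foresees patients leaving sooner, and no binary coding is safe if discharge timing differs between cohorts. Under an assumed 10% versus 30% leaving at day 2 and no drug effect, the false difference runs from 12 points in one direction to 2 in the other, against a planned effect of about 13 points. This rests on exponential times, on discharge unrelated to bowel function, and on discharge fractions that the documents do not supply. With equal fractions the false difference vanishes and only the absolute incidences are wrong.

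The case does not extend to replacing the definition with a composite that counts rescue as constipation. With multipliers of 1.5 to 2, the composite produces a larger false difference (2.1 to 4.7 points) than the current definition (1.0 to 3.4 points); at a multiplier of 3 with rescue at 48 hours the order reverses. That is a choice of estimand, not a correction. The primary outcome is not affected by this point.

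**What to change.** - In I. Study Design, keep the three-day definition and state that it means no BM in the 72 hours from start of surgery, in both cohorts. This is the time origin the Analysis Plan already uses for the primary outcome.
- In the Analysis Plan, take this outcome out of the general mixed-model sentence. Estimate the proportion BM-free at 72 hours by Kaplan-Meier in each cohort, censor patients discharged BM-free at discharge, and compare the cohorts with standard errors that respect the matched strata, for example by resampling matched sets.
- Report, by cohort, how many patients were discharged BM-free before 72 hours, with sensitivity analyses scoring them all as constipated and all as not constipated.
- Report the composite of no BM by 72 hours or laxative escalation before the first BM as a supplementary analysis only, since it also depends on each cohort's rescue practice.

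The cost is modest and needs no extra patients. Time to first BM and length of stay are already outcomes. The supplementary analysis needs the times of laxative escalations, including from historical records, whereas the plan lists only their number. The main analysis adds an assumption that discharge is non-informative, which the two extreme scorings bracket.

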### Toxicities and guidelines for adjustments

Potential adverse effects associated with the use of enteral naloxone have been associated with abrupt reversal of opioid activity with the most uncomfortable or dangerous of these being antagonism of central opioid activity and loss of pain control. Additional adverse effects include nausea, vomiting, diarrhea, hypertension, tachycardia, diaphoresis, and mental status changes. Patients will be monitored for adverse effects via routine vital signs, pain score, and neurological assessment every 1 – 4 hours and evaluation for emesis, bowel movements, and diaphoresis. Study drug will be discontinued in patients who meet any three of six criteria within 1 hour of study drug administration:

1. Heart rate increases > 20 beats per minute for > 5 minutes
2. Respiratory rate increases to > 20 breaths per minute
3. Diaphoresis
4. Pain score increases by > 50%
5. Emesis
6. Diarrhea (defined as > 1 large, liquid bowel movement within 1 hour)

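### Pain and opioid use on post-operative day 0 are pre-drug values listed as outcomes, and the plan states no baseline adjustment for them in the comparison with historical controls

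*Combined protocol and SAP*

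**What the plan says.** All references are to the combined protocol and SAP.

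- **Study Design** lists as a secondary outcome the "average numerical pain scale (Adult Nonverbal Pain scale or Visual Analog Scale) on post-operative days 0, 1, 2, and 3". Daily opioid use in morphine equivalents is listed for the same four days.
- **Study Assessments and Activities** says that oral naloxone "will be initiated on post-operative day 1 at 0900".
- **Study Design** describes the comparison: "This is a prospective, historically controlled observational trial of enteral naloxone use". **Screening procedures** takes the controls from a report of spinal fusion patients "identified via ICD9 codes in the previous 3 years", and gives the matching factors: "The historical controls will be matched to active participants based on age, gender, Charleston co-morbidity index, complexity of surgery, and duration of surgery".
- **Analysis Plan** compares the cohorts on every secondary outcome except length of stay with a generalized linear mixed model. The one feature it states is a random intercept per matched stratum. It names no baseline covariate and no term for day.
- **Study Aims** makes safety an aim: "The current study will assess the safety and efficacy of an enteral formulation of the opioid antagonist naloxone". **Toxicities and guidelines for adjustments** describes "the most uncomfortable or dangerous of these being antagonism of central opioid activity and loss of pain control" among the potential adverse effects.

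**The concern.** POD 0 ends before the first dose, so a cohort difference on that day says nothing about naloxone. It does show whether the cohorts already differed in pain or opioid use before treatment. The plan lists it as an outcome and gives it no baseline role.

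In a randomised trial this would mainly cost precision. Here the controls come from an earlier period, and neither pain nor opioid use is a matching factor. A random intercept per stratum accounts for correlation within a matched set. It does not correct a systematic difference between cohorts on a variable that was not matched.

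At stake is the between-cohort evidence on whether enteral naloxone weakens analgesia. If the naloxone cohort starts with less pain, a real worsening on POD 1–3 can be hidden. If it starts with more, a worsening can appear that the drug did not cause. The drug discontinuation criteria do not fill the gap, because they apply to treated patients only and give no comparison with controls.

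**Working it through.** **The plan's own figure.** The only power stated is 80.1%, for time to first bowel movement. Expected events are 150 × (1 − 0.45) + 150 × (1 − 0.30) = 187.5. The Schoenfeld formula gives z = (√187.5 / 2) × ln 1.508 − 1.960 = 2.812 − 1.960 = 0.852, which is power of 80.3%. With the hazard ratio taken as 0.241 / 0.160 = 1.506 it is 80.1%. The figure reproduces and has no bearing on pain or opioid use, for which no figure is stated.

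**Timing.** The plan does not define POD 0, but on any usual meaning the whole of it precedes 0900 on POD 1. On a calendar-day reading, 9 of the 24 hours of POD 1 (37.5%) are pre-drug as well.

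**Inputs for the size.** From the documents: 150 per cohort, two-sided alpha 0.05. Assumed: SD of 1, a POD 0 cohort difference d of 0.1, 0.2 or 0.3 SD, a correlation r between POD 0 and a later day of 0.2, 0.5 or 0.7, and each later day tested separately. The correlation induced by matching is ignored.

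**Formulas.** The unadjusted standard error is √(2/150) = 0.1155. If the POD 0 difference reaches later days only through its correlation with them, the unadjusted bias is r × d. With POD 0 as covariate, the standard error is √[(1 − r²)(2/150 + d²/298)], which for d = 0.3 is 0.1144 / 0.1011 / 0.0834. The rejection rate is Φ(b/SE − 1.96) + Φ(−b/SE − 1.96), where b is the bias.

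**(a) No drug effect, difference carries over through POD 0, no adjustment**

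| d | Bias at r = 0.2 / 0.5 / 0.7 | False positives per daily test |
|---|---|---|
| 0.1 | 0.02 / 0.05 / 0.07 | 5.3% / 7.2% / 9.3% |
| 0.2 | 0.04 / 0.10 / 0.14 | 6.4% / 13.9% / 22.8% |
| 0.3 | 0.06 / 0.15 / 0.21 | 8.1% / 25.5% / 44.4% |

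Adjustment removes this bias. In 4000 simulated trials at d = 0.3 the adjusted rates were 5.7% / 5.0% / 4.8%.

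**(b) Hidden harm, d = 0.3.** A true worsening of 0.3 SD is detected 73.8% of the time per day with no imbalance. If the naloxone cohort starts 0.3 SD lower and this carries over, the net difference is 0.3 − 0.3r = 0.24 / 0.15 / 0.09. Detection is 54.7% / 25.5% / 12.2% unadjusted and 74.6% / 84.3% / 94.9% adjusted.

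**(c) Era difference of 0.3 SD on every day, no drug effect.** The unadjusted false-positive rate is 73.8%. The adjusted bias is 0.3 × (1 − r) = 0.24 / 0.15 / 0.09, giving 55.5% / 31.7% / 19.0%. Adjustment reduces the error and does not restore 5%.

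**(d) Adverse case: a 0.3 SD difference on POD 0 that does not carry over.** The unadjusted test keeps 5%. Adjustment introduces a bias of −0.3r, and false positives are 8.2% / 31.7% / 71.2%.

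**(e) No imbalance.** Adjustment is worth 1/(1 − r²) = 1.04 / 1.33 / 1.96 times the sample size in a daily test.

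**The case against.** **The plan is silent rather than wrong.** It nowhere says that a POD 0 difference will be read as a drug effect. One sentence covers nearly all secondary outcomes and states no fixed effects beyond the group comparison, so a POD 0 covariate is not ruled out, and showing POD 0 by cohort is reasonable. This stands in part. A reader might infer that POD 0 will be averaged with later days, or that all days will be pooled with no patient term. The documents propose neither, so no size is claimed for those cases. What remains is more than missing detail: POD 0 is listed as an outcome, and in an unblinded comparison with historical controls the covariates should be fixed before results are seen.

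**The size is assumed.** This stands. Nothing in the documents favours 0.3 SD over 0.1 SD, and matching on age, comorbidity, complexity and duration of surgery may keep the imbalance small. At 0.1 SD the effect is minor.

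**Adjustment can do harm.** This stands too. Take d = 0.3 with only half of the expected amount carried over. The bias is then equal in size either way, but the adjusted standard error is smaller: false positives are 11.5% adjusted against 10.0% unadjusted at r = 0.5, and 24.2% against 14.9% at r = 0.7. With less than about half carried over, adjustment is the worse choice. The documents cannot say which case applies, so both results are needed.

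**Pain has two permitted scales.** The outcome allows either the Adult Nonverbal Pain scale or the Visual Analog Scale, and no conversion is given. A patient may be scored on one on POD 0 and the other later, so a single linear covariate may not be valid for pain. This stands, and the fix allows for it.

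**Conclusion.** The concern holds. Confidence is high that POD 0 precedes the drug and that no baseline adjustment is stated. It is not high on the size, which rests wholly on an assumed SD, correlation, imbalance and degree of carry-over. With full carry-over, unadjusted false positives per daily test run from about 5% (0.1 SD, r = 0.2) to 44% (0.3 SD, r = 0.7), against about 5% adjusted.

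Three stronger readings are not supported:

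- A reader might infer that the pain comparison will probably mislead. The documents do not show that any imbalance exists.
- A reader might infer that adjusting for POD 0 makes the historical comparison sound. Cases (c) and (d) show that it does not.
- A reader might infer that the main result is at risk. The point concerns two secondary outcomes. The primary analysis and its 80.1% power are unaffected.

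The change should be made because safety is a stated aim and these outcomes are the most direct between-cohort measure of loss of pain control.

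**What to change.** 1. Treat POD 0 pain and morphine equivalents as baseline. Report them by cohort only as a balance check.
2. Analyse POD 1–3 pain and morphine equivalents with the patient's POD 0 value as a covariate. For pain, do this only where POD 0 and the later day use the same scale, or include a term for scale.
3. Report the unadjusted POD 1–3 comparison beside the adjusted one, and say in advance how a disagreement will be described.
4. State how a post-operative day is bounded, and whether the later days are tested separately or jointly.
5. State as a limitation that adjustment for POD 0 reduces but does not remove era differences, and can add bias if the POD 0 difference does not persist.

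The cost is SAP wording, one covariate from values already listed for collection, and a record of which pain scale was used on each day. There is no added burden on patients and no change to the sample size.
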